**CLINICAL PROTOCOL SYNOPSIS**

Title of study: Efficacy, Safety, and Tolerability of GLS-1200 Topical Nasal Spray in the Prevention of Incident Confirmed SARS-CoV-2 Infection																					
Number of study sites and Countries/Regions: 2, US																					
Target Number of study participants: 225																					
Study Phase: II																					
Study Type: Randomized, placebo-controlled, double-blind																					
Research Hypothesis: GLS-1200 topical nasal spray will be well tolerated and can reduce the incidence of confirmed SARS-CoV-2 infection																					
Primary study objectives and outcome variables: 
 
Evaluate the safety and tolerability of GLS-1200 topical nasal spray
 
Incidence of SARS-CoV-2 infection, confirmed by PCR relative to treatment group
 
																					
Secondary study objectives and outcome variables: 
 
Documentation of symptoms consistent with SARS-CoV-2 infections relative to treatment group
 
																					
Exploratory study objectives and outcome variables: 
 
Incidence of SARS-CoV-2 seroconversion relative to treatment group
 
Assess the relationship of taste receptor genetics to incidence of SARS-CoV-2 infection and relative to treatment group
 
																					
Table S1: Dosing arms and treatment regimen																					

  
 Group	N	Treatment assignment	Study drug	Diluent	Spray volume	Treatment schedule	
   
 1	150	GLS-1200	1 mg/mL quinine sulfate, dihydrate	0.9% sterile saline	1 mL/nostril	TID x 4 weeks	
 
 2	75	Placebo (0.9% sterile saline)	0.9% sodium chloride solution	N/A	1 mL/nostril	TID x 4 weeks	
  
	Group	N	Treatment assignment	Study drug	Diluent	Spray volume	Treatment schedule	1	150	GLS-1200	1 mg/mL quinine sulfate, dihydrate	0.9% sterile saline	1 mL/nostril	TID x 4 weeks	2	75	Placebo (0.9% sterile saline)	0.9% sodium chloride solution	N/A	1 mL/nostril	TID x 4 weeks
Group	N	Treatment assignment	Study drug	Diluent	Spray volume	Treatment schedule															

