## **3. STUDY DESIGN**

This is a Phase II, placebo-controlled, double-blind study of GLS-1200 topical nasal spray to assess the safety, tolerability, and ability to reduce the incidence of confirmed SARS-CoV-2 infection. Following recruitment and informed consent, those meeting enrollment criteria will be randomized 2:1 (GLS-1200:placebo). Participants will initiate topical nasal spray applications immediately after randomization and will continue for 4 weeks. Participants will self-administer drug three times daily. The primary outcome measurements are safety, tolerability, and reduction in the diagnosis of PCR-confirmed SARS-CoV-2 infection. Follow-up will continue through 6 weeks since some cases of SARS-CoV-2 infection may not be apparent until after the primary treatment period has concluded. Secondary measures will assess the incidence of symptoms between each visit, by treatment group. In addition the average number of days subjects experience each symptom will be summarized by treatment group. Exploratory measures will assess the incidence of seroconversion in serum and the relationship of taste receptor genetics to incidence of SARS-CoV-2 infection both relative to treatment group.

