#### **4.3 Exclusion Criteria**

1. Known allergy to quinine, quinidine or mefloquine
2. Confirmed prior positive test for SARS-CoV-2
3. Treatment within the past 2 weeks with chloroquine, hydroxychloroquine, or remdesivir
4. Pregnancy or documentation of pregnancy by pre-treatment urine pregnancy test or breast feeding or plans to become pregnant during the course of the study

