**Results of the Nasopharyngeal Swab**

Results of the nasopharyngeal swab may be received as soon as one day after testing.

If the PCR results are positive for SARS-CoV-2 infection at enrollment, the participant will be asked to remain in the study, administer study drug as per protocol, comply with all required testing for safety, and complete the remaining visits. If the participant does not want to administer study drug or complete testing, they will be asked to consent to telephone contact for the remaining visits.

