## **8. EFFICACY ANALYSES**

### **8.1. Definition of the Primary Efficacy Endpoint**

The primary efficacy endpoint is the incidence of SARS-CoV-2 infection, confirmed by PCR at any time within four weeks of treatment initiation. Participants will be queried as to any new diagnosis of SARS-CoV-2 infection, defined as a positive PCR test for SARS-CoV-2. Subjects who test negative for SARS-CoV-2 infection at Weeks 2 and 4 will be considered treatment successes. Subjects who are lost to follow-up, require rescue therapy, discontinue the study prior to completion of Week 4, or test positive for SARS-CoV-2 infection at any point within four weeks of treatment initiation will be considered treatment failures. All deaths will be considered as treatment failures.

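### No efficacy set requires a negative Day 0 PCR, so infections present before the first dose can count as failures to prevent incident infection

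*SAP*

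**What the plan says.** The study title in the Protocol synopsis sets the aim: "Topical Nasal Spray in the Prevention of Incident Confirmed SARS-CoV-2 Infection". Protocol 4.3 excludes people with a "Confirmed prior positive test for SARS-CoV-2", which covers only infection already known.

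The Day 0 swab cannot act as a gate. Protocol 3 states: "Participants will initiate topical nasal spray applications immediately after randomization and will continue for 4 weeks". Protocol 6.5 says of the result: "Results of the nasopharyngeal swab may be received as soon as one day after testing". It then says: "If the PCR results are positive for SARS-CoV-2 infection at enrollment, the participant will be asked to remain in the study". A Day 0 positive who "does not want to administer study drug or complete testing, they will be asked to consent to telephone contact for the remaining visits".

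The scoring rules are:

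- **Positive PCR.** SAP 8.1 lists among the failures those who "test positive for SARS-CoV-2 infection at any point within four weeks of treatment initiation will be considered treatment failures". Protocol 8.1 names positives at Week 2 or Week 4.
- **Missing PCR.** Protocol 8.8 makes a missing primary assessment a failure, and SAP Table 14.2.1.1 has a failure row for it.
- **Success.** "Subjects who test negative for SARS-CoV-2 infection at Weeks 2 and 4 will be considered treatment successes" (SAP 8.1, repeated in footnote [2] of Table 14.2.1.1).

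The ITT set is everyone randomized (Protocol 8.1, SAP 6.1). The per-protocol set requires trial completion, at least 90% of doses and no significant deviation (SAP 6.3). SAP 8.2 applies the primary analysis to these two sets only. The Day 0 result is tabulated in Table 14.2.1.1, but it defines neither a set nor the endpoint.

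**The concern.** An infection present before the first dose cannot be prevented by the spray. Under these rules it still counts as a failure by either of two routes: the participant is still PCR-positive at Week 2 or 4, or has no PCR at one of those visits. Protocol 6.5 itself feeds the second route, because telephone contact yields no study swab. A Day 0 positive who stays as asked breaches no per-protocol criterion on that account, so the per-protocol analysis does not remove the problem.

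Randomization balances Day 0 positivity on average, but not what happens to it afterwards. If the same share of Day 0 positives ends as failures in each arm, the relative risk moves towards 1 and power falls. If the drug changes clearance, an effect on existing infection is mixed with prevention, in either direction. The protocol leaves that possibility open. Section 1.1 postulates an effect on both incidence and severity, and the influenza experiment in 1.1.1.2 dosed cells after infection.

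A smaller point concerns Table 14.2.1.1. Its positive-PCR and missing-PCR rows run up to Week 4 with no lower time limit, beside a Week 0 block. Programmed literally, they would make a failure of someone positive only at Day 0, or missing only the Day 0 swab, although the success rule makes a success of anyone negative at Weeks 2 and 4.

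**Working it through.** **Inputs from the documents.** 150 GLS-1200 and 75 placebo; infection 1% and 10%; alpha 0.05; stated power 80.8% (Protocol 8.7, SAP 4); Fisher's exact test (SAP 8.2).

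**Inputs the documents do not give, so assumed.** q = share PCR-positive at Day 0; r = share of Day 0 positives who end as failures because of that infection; d = rate of other composite failures (loss, discontinuation, rescue, death, missing PCR).

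**Reproducing the plan's figure.** I enumerated both binomials in full and rejected when either hypergeometric tail was 0.025 or less. This gives 80.9% against the stated 80.8%, and all six rows of Protocol Table 8.7-1 agree within 0.4 points. Square brackets below use the usual two-sided Fisher p-value of 0.05 or less instead, which gives [87.6%] for the planned case.

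**Formula.** Failure rate per arm = d + (1 − d) × [q·r + (1 − q)·p], with p = 1% or 10%. After exclusion the rate is d + (1 − d)·p, and power is averaged over the binomial number of Day 0 positives removed from each arm.

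**Example, d = 0, q = 2%, r = 50%.**

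- Placebo: 0.02 × 0.5 + 0.98 × 0.10 = 10.8%.
- GLS-1200: 0.02 × 0.5 + 0.98 × 0.01 = 1.98%.
- Apparent relative reduction: 1 − 1.98/10.8 = 82%, against the planned 90%.

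**Power (%) with Day 0 positives kept or excluded.**

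| d | q | kept, r = 0 | kept, r = 25% | kept, r = 50% | excluded |
|---|---|---|---|---|---|
| 0 | 2% | 79.9 [87.0] | 74.6 [81.6] | 69.6 [76.9] | 79.9 [87.0] |
| 5% | 2% | 43.7 [49.8] | 42.1 [48.1] | 40.7 [46.6] | 44.8 [50.3] |

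The gain from exclusion is therefore 0 / 5 / 10 points at d = 0, and 1.1 / 2.7 / 4.1 points [0.6 / 2.2 / 3.7] at d = 5%. The roughly 1 point at r = 0 and d = 5% comes partly from the discreteness of the exact test and should not be credited to the fix.

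**Gain in points for other values.**

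| d | q | r = 25% | r = 50% |
|---|---|---|---|
| 3% | 2% | 3.3 [3.4] | 5.4 [5.9] |
| 10% | 2% | 1.3 [2.1] | 1.9 [2.8] |
| 5% | 1% | 1.7 [1.2] | 2.5 [2.0] |
| 5% | 5% | 5.2 [5.0] | 8.0 [8.4] |

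**Unequal persistence, d = 0, q = 2%.** With r = 25% on GLS-1200 and 50% on placebo, power is 78.1% [84.4]. With the values reversed it is 65.5% [73.4].

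**No effect on incident infection** (10% in both arms, d = 0, r = 0 on GLS-1200 and 50% on placebo). The rejection rate is 3.3% [4.6] at q = 2% and 5.8% [7.8] at q = 5%, against 2.75% [3.7] with no Day 0 positives.

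**Counts.** The plan expects 150 × 1% = 1.5 infections on GLS-1200. Expected Day 0 positives in that arm are 150 × q = 1.5, 3.0 and 7.5 at q = 1%, 2% and 5%.

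**The case against.** - **It is a deliberate, visible choice of estimand.** Protocol 6.5 keeps Day 0 positives in, Protocol 8.1 names ITT for the primary outcome, and the table shell and the PCR listing show Day 0 results. This is true, and it means a reader could trace those cases afterwards. It does not change what the primary test counts.
- **The endpoint already speaks of incidence and asks about new diagnoses.** That wording describes a query put to participants. The failure rule, the set definitions and the table shell do not carry it through.
- **The size is assumed, and the largest gains need d = 0.** This stands. Setting d = 0 while missing swabs feed r means that only Day 0 positives ever miss a swab. With q = 0, raising d from 0 to 5% alone takes power from 80.9% to 45.0% [87.6 to 51.1], so the composite and missing-as-failure rules matter far more than Day 0 positives.
- **With equal persistence the present rule is conservative, and the inflated rejection rate needs extreme inputs.** Also fair. Only the scenario with q = 5% and persistence of 0 against 50% exceeds 5%, and the evidence for unequal persistence is thin: influenza in cell cultures from two patients.
- **A sensitivity analysis would be enough.** It would recover much of the interpretation. The case for making the restriction primary is that it rests on a pre-treatment swab, adds no post-randomization selection and fits the stated aim. Which analysis leads is partly a judgement.

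**Conclusion.** The concern holds. Followed exactly, the plan scores some infections that predate treatment as failures to prevent incident infection, and neither efficacy set removes them. A participant positive only at Day 0 and negative at Weeks 2 and 4 is a success, so for that person only the table-label ambiguity remains.

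The consequence is probably modest. Over the scenarios with 3% to 10% other failures, q of 1% to 5% and r of 25% or 50%, exclusion gains about 1 to 8 points of power. At q = 2% with no other failures it gains 5 to 10 points. All of this rests on assumed q, r and d. The interpretive gain does not depend on those values: a difference in the restricted set cannot come from clearing an infection already detected at Day 0. This is an inexpensive improvement, not a fatal flaw, and is held with medium confidence because the size is unknown.

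**What to change.** In SAP 6 and 8.1–8.2:

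- Define the primary efficacy set as randomized participants without a positive Day 0 PCR.
- Retain those with a missing Day 0 result, and add a sensitivity analysis that excludes them.
- Count as infection only the first positive PCR after Day 0.
- In Table 14.2.1.1, limit the positive row to results after Day 0 and the missing-PCR row to Weeks 2 and 4.
- Keep the all-randomized analysis as a sensitivity analysis, and record the departure from Protocol 8.1. Protocol 8 provides for the SAP to modify the analysis plan.

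This concerns the analysis only and asks for no change in how Day 0 positives are managed.

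The cost is SAP wording, one population flag, one rule for missing Day 0 results, two row labels and two repeats of one table. No new data are needed. At q = 1% to 5%, about 2 to 11 of 225 participants (225 × q = 2.25 to 11.25) leave the primary set. They stay in the all-randomized sensitivity analysis, and their place in the safety analysis does not change. The primary set is then no longer everyone randomized. Infections incubating but PCR-negative at Day 0 would still count, so the restriction restores the incident meaning only in part.

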### **8.2. Analysis of the Primary Efficacy Endpoint**

The number and percentage of treatment failures as well as treatment successes will be presented by treatment and compared using Fisher's exact test. Additionally, the number and percentage of subjects who test positive as well as those who test negative for SARS-CoV-2 infection will be provided by treatment at each visit (Weeks 2, 4 and 6). This summary and analysis will be performed for both the ITT and PP populations.

### **8.3. Definition of the Secondary Efficacy Endpoint**

The secondary efficacy endpoint is the documentation of symptoms consistent with SARS-CoV-2 infections. Subjects will be instructed to maintain a symptom diary that includes those symptoms considered common for SARS-CoV-2. The diary is inclusive of symptoms identified by the World Health Organization for a diagnosis of SARS-CoV-2 as well as more recently identified symptoms such as conjunctivitis, diarrhea, and loss of taste or smell. Each symptom will be scored as present (score of 1) or absent (score of 0) and will be recorded in the symptom diary on a daily basis.

### **8.4. Analysis of the Secondary Efficacy Endpoint**

The incidence of each symptom will be summarized by treatment group for each two week interval. In addition, the average number of days subjects had each symptom throughout the study period (6 weeks) will be summarized by treatment group. Summaries will be presented noncumulatively by visit as well as cumulatively over 4 weeks of treatment. The secondary analysis will be performed for the ITT population.

## **8.5. Definition of the Exploratory Efficacy Endpoint**

The exploratory efficacy endpoint is the incidence of SARS-CoV-2 seroconversion.

## **8.6. Analysis of the Exploratory Efficacy Endpoint**

The cumulative number and percentage of subjects who seroconvert at each post-baseline visit will be presented by treatment for the ITT population. The relationship of taste receptor genetics to incidence of SARS-CoV-2 infection relative to treatment group will be examined on an adhoc basis and is outside the scope of this document.

# **9. SAFETY ANALYSES**

All safety analyses will be based on the Safety Population.

## **9.1. Adverse Events**

An adverse event (AE) is defined as any unfavorable and unintended change in the structure, function, or chemistry of the body, or worsening of a pre-existing condition, temporally associated with the use of a product whether or not considered related to the use of the product. In this study, such changes will be monitored, classified, and summarized, as Clinical or Laboratory AEs. Medical conditions/diseases present before starting the investigational drug will be considered adverse events only if they worsen after starting study treatment. Verbatim terms on CRFs will be mapped to preferred terms (PTs) and system organ classes (SOCs) using the Medical Dictionary for Regulatory Activities (MedDRA) (version 23.0).

### **9.1.1. Severity**

AEs are graded by the investigator as Grade 1 (mild), Grade 2 (moderate), Grade 3 (severe), Grade 4 (potentially life threatening) or Grade 5 (death) according to the NCI Common Terminology Criteria for Adverse Events version 5.0.

### **9.1.2. Relationship**

Based on the criteria described below, AEs will be classified according to one of the following categories:

- Related – the investigator considers that there is a causal relationship between the event and study drug
- Probably related – the investigator considers that there is a probability of a causal relationship of the event to the study drug
- Possibly related – the investigator considers that there is a possible causal relationship of the event to the study drug
- Unlikely related – the investigator considers that there is an unlikely causal relationship of the event to the study drug
- Not related – the investigator considers that the event has no relationship to administration of the study drug

For the purpose of analysis, related AEs are those reported as "Related," "Probably related," "Possibly related" and unrelated AEs are those reported as "Unlikely related" or "Not related." Events for which the investigator did not record relationship will be considered related for analysis. Data listings will show relationship as missing.

### **9.1.3. Serious Adverse Events**

An SAE is any adverse drug experience occurring at any dose that results in any of the following outcomes:

- Death during the period of surveillance defined by the protocol;
- Is immediately life-threatening (e.g., participant was, in the view of the Investigator, at immediate risk of death from the event as it occurred). This does not include an AE that, had it occurred in a more serious form, might have caused death;
- An event requiring inpatient hospitalization or prolongation of existing hospitalization during the period of protocol defined surveillance (including any overnight stay in the hospital, regardless of the length of stay, even if the hospitalization is only a precautionary measure to allow continued observation. However, hospitalization (including hospitalization for an elective procedure) for continued treatment or assessment of a pre-existing condition that has not worsened, does not constitute an SAE. NOTE: Evaluation in a physician's office, or at a hospital or other urgent care setting in an observational, non-admitted status regardless of the time period of observation, does not constitute an SAE;
- Results in congenital anomaly or birth defect;
- Results in persistent or significant disability/incapacity or substantial disruption of the ability to conduct normal life functions;
- Is an important medical event that may not result in death, be life threatening, or require hospitalization, but based upon appropriate medical judgment, may jeopardize the participant and may require medical or surgical intervention to prevent one of the outcomes listed above. Examples of such medical events include allergic bronchospasm requiring intensive treatment in an emergency room or at home, blood dyscrasias or convulsions that do not result in inpatient hospitalization;
- Is medically significant or requires intervention to prevent one or other of the outcomes listed above.

### **9.1.4. Treatment-Emergent Adverse Events (TEAEs)**

#### **9.1.4.1. Definition of Treatment-Emergent**

TEAEs are events that either:

- a) began on or after the date and time of first dose or

b) had no recorded start date and the stop date is not before the date and time of first dose.

#### 9.1.4.2. Incomplete Dates

If the date of onset is incomplete, then the month and year (or year alone if month is not recorded) of onset determine treatment emergence as follows. The event is treatment emergent if the month and year of onset (or year of onset) of the event is the same as or after the month and year (or year) of date of first dose.

### 9.1.5. Summaries of Adverse Events

An overall summary of AEs will display, by treatment, the number and percentage (with 95% exact binomial confidence interval) of subjects who had any TEAE, whose strongest TEAE relationship to study drug is related or not related, whose maximum TEAE severity is mild, moderate, or severe, who had any SAE, any Serious TEAE, any TEAE leading to study discontinuation, and any TEAE leading to death.

The following summaries (number and percentage of subjects) of AEs (by SOC and PT) will be provided by treatment:

- All TEAEs
- All TEAEs by strongest relationship
- All TEAEs by maximum severity grade
- All Serious AEs
- All Serious TEAEs
- All TEAEs leading to study discontinuation
- All TEAEs leading to death

These summaries will present the number and percentage of subjects with at least one qualifying AE. Subjects may have more than one AE per SOC and PT. Each summary will be ordered by descending order of incidence of SOC and PT within each SOC.

In addition to the by-treatment summaries, data listings will be provided for the following:

- All AEs (with a flag indicating whether the event is treatment emergent)
- SAEs
- AEs leading to study discontinuation
- Deaths

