1	150	GLS-1200	1 mg/mL quinine sulfate, dihydrate	0.9% sterile saline	1 mL/nostril	TID x 4 weeks															
2	75	Placebo (0.9% sterile saline)	0.9% sodium chloride solution	N/A	1 mL/nostril	TID x 4 weeks															
Study design: This Phase II randomized, placebo-controlled, double-blind study will assess whether topical GLS-1200 applied via nasal spray atomizer is well-tolerated and can reduce the incidence of confirmed SARS-CoV-2 infection. Subjects will be randomized to either GLS-1200 or placebo group in a 2:1 ratio with a target enrollment of 225 subjects. Subjects will self-administer study drug three times daily (TID) for 4 weeks.																					
Safety assessments: Participants will be monitored for adverse events. Laboratory and electrocardiographic (ECG) safety assessments will be performed at baseline and at the completion of 4 weeks of treatment. Subjects will complete a diary with daily entries to document clinical symptoms consistent with SARS-CoV-2 infection.																					
Study population:																					
Inclusion criteria:																					

 
Age 18 years or older
 
Able to provide informed consent
 
Able and willing to comply with study procedures
 
Able and willing to utilize an approved form of pregnancy prevention for women of child-bearing potential through to the end of treatment.
 
																					
Exclusion criteria:																					

 
Known allergy to quinine or quinidine or mefloquine
 
Confirmed prior positive test for SARS-CoV-2
 
																					

3. Treatment within the past 2 weeks with chloroquine, hydroxychloroquine, or remdesivir
4. Pregnancy or documentation of pregnancy by pre-treatment urine pregnancy test or breast feeding or plans to become pregnant during the course of the study

Table S2: Schedule of Events

Tests and Observations	Day 0	Week 2	Week 4	Week 6	Unscheduled
Permitted window (days)		±3d	±3d	±3d	N/A
Clinical Evaluations					
Obtain Written Informed Consent	X				
Confirm Eligibility Criteria	X				
Demographics	X				
Medical History and Concomitant Medications	X	X	X	X	
Physical Exam, height, weight, and Vital Signs 	X	X	X	X	X
Safety Evaluations					
Record Adverse Events		X	X	X	X
Provide participant diary	X				
Collect and review participant diary		X 	X	X	

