### **8.3.1 Adverse events**

Treatment emergent AEs will be summarized by frequencies and will be presented by system organ class and preferred term with the number and percentage of participants affected. Frequencies will be presented with respect to maximum severity and to strongest relationship to Study Treatment. Multiple occurrences of the same AE will be counted only once following a worst-case approach with respect to severity and relationship to Study Treatment.

The proportion of participants experiencing any AEs (Grade 1-4) following treatment with study drug will be presented as part of the safety analysis set. The precision with which this sample result estimates the rate of similar AEs in the population represented by the study sample will be reported in terms of 95% confidence intervals (CI) around the sample proportions. This will provide 95% confidence that the rate of severe adverse effects is not greater than the upper limit of the CI around the proportion of participants with grade 3+ events in the study sample.

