**Table 8.7-1 Range of treatment rates detectable with at least 80% power**

Treated Infection Rate (N=150)	Placebo Infection Rate (N= 75)	Difference Treated - Placebo	Actual Power
0	7.3%	-7.3%	80.3%
1%	10%	-9%	80.8%
2.5%	13.5%	-11%	80.3%
5%	18.1%	-13.1%	80.4%
7.5%	22.1%	-14.6%	80.3%
10%	25.7%	-15.7%	80.0%

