## 2. STUDY OBJECTIVES

### 2.1. Primary Objectives

The primary objectives of the study are to evaluate the safety and tolerability of GLS-1200 topical nasal spray as well as the incidence in the diagnosis of PCR-confirmed SARS-CoV-2 infection by treatment group.

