## 3. STUDY DESIGN AND PLAN

This is a Phase II, placebo-controlled, double-blind study of GLS-1200 topical nasal spray to assess the safety, tolerability, and ability to reduce the incidence of confirmed SARS-CoV-2 infection. Following recruitment and informed consent, those meeting enrollment criteria will be randomized 2:1 (GLS-1200:Placebo). Participants will initiate topical nasal spray applications immediately after randomization and will continue for 4 weeks. Participants will self-administer drug three times daily. Follow-up will continue through 6 weeks since some cases of SARS-CoV-2 infection may not be apparent until after the primary treatment period has concluded. The primary outcome measurements are safety, tolerability, and reduction in the diagnosis of PCR-confirmed SARS-CoV-2 infection. Secondary measures will assess the incidence of symptoms

between each visit, by treatment group. In addition the average number of days subjects experience each symptom will be summarized by treatment group. Exploratory measures will assess the incidence of seroconversion in serum and the relationship of taste receptor genetics to incidence of SARS-CoV-2 infection both relative to treatment group.

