#### **4. DETERMINATION OF SAMPLE SIZE**

The sample size for this study assumes an infection rate in the placebo group of 10%. A 2:1 randomization of 225 subjects would have a power of 80.8% to detect a difference of 9% between groups at alpha = 0.05 assuming 1% of individuals in the treatment group are confirmed to be infected with SARS-CoV-2.

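### Safety is a primary objective of a placebo-controlled trial, but no planned display estimates the excess of adverse events on GLS-1200 over placebo with its uncertainty

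*SAP*

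**What the plan says.** SAP 2.1 puts safety first: "The primary objectives of the study are to evaluate the safety and tolerability of GLS-1200 topical nasal spray", together with the incidence of PCR-confirmed infection by treatment group. Protocol 2.2 lists the same two items, and protocol 2.1 hypothesises that the spray will be safe and well tolerated. SAP 3 describes the design: "This is a Phase II, placebo-controlled, double-blind study of GLS-1200 topical nasal spray to assess the safety, tolerability, and ability to reduce" infection. The protocol synopsis gives the allocation: "Subjects will be randomized to either GLS-1200 or placebo group in a 2:1 ratio with a target enrollment of 225 subjects", that is, 150 and 75.

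For adverse events, SAP 9.1.5 states: "An overall summary of AEs will display, by treatment, the number and percentage (with 95% exact binomial confidence interval) of subjects" in each category. Shell 14.3.1.1 puts n, % and the exact 95% CI in one column per arm and has no difference column. Protocol 8.3.1 says that precision "will be reported in terms of 95% confidence intervals (CI) around the sample proportions", and uses the upper limit to bound the rate of severe (grade 3 or higher) events.

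The other safety displays are also by arm: n and % for the system organ class and preferred term tables, shift tables for laboratory results and ECG interpretation, category counts for QTcF, and descriptive statistics for vital signs. Neither document gives a risk difference, ratio, test or between-arm interval for any safety variable. The only between-arm test is Fisher's exact test on the primary efficacy endpoint (SAP 8.2).

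**The concern.** Protocol 1.4 says that the adverse effects of topical quinine are unknown. The placebo arm is therefore this trial's own reference for what the drug adds to a saline spray. That is a two-arm question, and the planned intervals answer a one-arm question: how precisely is each arm's rate known?

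With only those intervals on the page, a reader who wants to judge the arms against each other is left to compare them by eye. Two 95% intervals can overlap when the 95% interval for the difference excludes zero. At stake is how clearly the report can say what excess of events is shown, and what excess remains compatible with the data, for a primary objective.

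**Working it through.** **Inputs.** From the documents: 150 on GLS-1200 and 75 on placebo (protocol synopsis and Table 8.7-1), and exact binomial 95% intervals per arm (SAP 9.1.5). Assumed: everyone randomised is dosed, so the Safety Population keeps these sizes. The documents give no adverse event rates for topical GLS-1200, so all rates below are assumptions, shown over a range.

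**The plan's own figure.** Neither document states a safety figure. The one stated operating characteristic is for efficacy (SAP 4): "A 2:1 randomization of 225 subjects would have a power of 80.8% to detect a difference of 9% between groups at alpha = 0.05", with 1% v 10%. Enumerating all 151 × 76 outcomes with a continuity-corrected z test at two-sided 0.05 gives 80.9%, against 80.8% stated. The arm sizes and the enumeration method therefore agree with the plan.

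**One worked table.** Take any TEAE in 45/150 (30.0%) v 12/75 (16.0%).

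- Exact (Clopper-Pearson) per-arm intervals: 22.8% to 38.0% and 8.6% to 26.3%. They overlap, because 22.8 < 26.3.
- Wilson limits, needed for the Newcombe interval: [p + z²/2n ± z√(p(1−p)/n + z²/4n²)] / (1 + z²/n) with z = 1.96. These are 23.24% to 37.76% and 9.40% to 25.92%.
- Difference: 0.300 − 0.160 = 0.140.
- Newcombe lower limit: 0.140 − √[(0.300 − 0.2324)² + (0.2592 − 0.160)²] = 0.140 − √(0.00457 + 0.00984) = 0.140 − 0.120 = 0.020.
- Newcombe upper limit: 0.140 + √[(0.3776 − 0.300)² + (0.160 − 0.0940)²] = 0.140 + √(0.00602 + 0.00436) = 0.140 + 0.102 = 0.242.

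The excess is 14.0 points (95% CI 2.0 to 24.2; Fisher p = 0.024), yet the planned display shows overlapping intervals. The same happens at 30/150 v 6/75 (difference 12.0 points, CI 1.9 to 20.3) and at 60/150 v 18/75 (16.0 points, CI 2.9 to 27.5).

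**How often.** Sum the two binomial probabilities over all outcomes. A is the probability that the Newcombe interval excludes zero, B the probability that the per-arm exact intervals are separate. Separation never occurred without A in this enumeration, so A − B is the probability that the difference interval excludes zero while the per-arm intervals overlap.

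| True rates, GLS-1200 v placebo (assumed) | A | B | A − B |
|---|---|---|---|
| 40% v 25% | 61.4% | 27.0% | 34.4% |
| 30% v 15% | 70.9% | 35.8% | 35.1% |
| 20% v 10% | 47.1% | 16.5% | 30.6% |
| 15% v 5% | 61.5% | 26.2% | 35.3% |

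**Where the remedy is weak.** The same enumeration for rarer events gives A = 20% at 10% v 5%, 8.9% at 5% v 2%, and 1.9% at 3% v 1%. With no true difference (20% v 20%), A is 4.8% per row, so a few rows among many will exclude zero by chance.

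**The case against.** The strongest reply is that the plan does what it sets out to do. The safety objective is to evaluate safety and tolerability; the words that tie an outcome to treatment group are attached to infection, not to safety. Protocol 8.3.1 gives the per-arm intervals a clear purpose, bounding each rate, and exact binomial intervals suit it. Protocol and SAP agree with each other. By-arm descriptive tables of adverse events are common. All of this stands.

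Three stronger readings are tempting, and the documents do not support them.

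- A reader might infer that a co-primary safety comparison was promised and then left untested. Neither document uses that term or states a comparative safety hypothesis, margin or tolerability threshold.
- A reader might infer that the plan will declare no difference when the intervals overlap. No such rule is written. The 31% to 35% figures describe how unreliable overlap would be as a guide; they are not error rates of a planned analysis.
- A reader might infer that the trial could not state the size of an excess at all. It could: both counts and denominators are printed, and the difference and its interval follow from them.

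It is also fair that a difference interval for rare events will usually include zero, and could itself be misread as reassurance. What survives is narrower. The plan already chose to give intervals for this table, the placebo arm exists to show what the drug adds, and leaving the difference to be derived afterwards leaves its method and rows open to choice after the data are seen.

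**Conclusion.** The gap is real and modest. A primary objective in a placebo-controlled trial has valid per-arm intervals but no planned estimate of the excess over placebo. For common events at the assumed rates (placebo 5% to 25%, excess 10 to 15 points), about a third of trials would show an excess on the difference scale that overlapping per-arm intervals would not make visible. For rare events the added interval would seldom exclude zero; its value there is to show how large an excess is still compatible with the data.

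This is a cheap improvement worth making, not an error that invalidates the safety analysis. It changes no endpoint, population, sample size or primary test. The figures rest on full arm sizes of 150 and 75, on assumed event rates, and on the Newcombe interval.

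**What to change.** Keep the per-arm exact intervals. Add to SAP 9.1.5 and Table 14.3.1.1 the risk difference, GLS-1200 minus placebo, with a 95% CI by one method named in advance (Newcombe or Miettinen-Nurminen). Do this at least for any TEAE, related TEAE, severe TEAE, any SAE, and TEAE leading to study discontinuation. Define the severe row as grade 3 or higher, to match the bound in protocol 8.3.1.

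Add two sentences to the SAP: that these intervals are descriptive estimates without control for multiplicity, and that an interval including zero does not show equal safety, especially for rare events.

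The cost is a few lines of text, one table column and several unadjusted intervals. No further participants, data or procedures are needed.
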